### **12.2.8 Safety Analysis(es)**

Safety analyses will be performed using the safety population according to the treatment that the subject received. Adverse events (AEs) will be coded using the Medical Dictionary for Regulatory Activities (MedDRA).

AEs will be regarded as treatment emergent if they occur on or after the first treatment application.

Treatment Emergent Adverse Events (by System Organ Class/Preferred Term), Treatment Emergent Adverse Events (skin site related/non-skin site related), treatment-related AEs (skin site related/non-skin site related) will be summarised overall and by treatment group.

Deaths, Non-fatal Serious Adverse Events, Treatment Emergent Adverse Events leading to study or drug discontinuation will be listed.

### **12.2.9 Handling of Dropouts and Missing Data**

Missing data will not be replaced or imputed. Dropouts will be included in analyses up to the point of discontinuation.

### **12.2.10 Interim Analysis**

No interim analysis is planned for this study.

## **13 STUDY GOVERNANCE CONSIDERATIONS**

### **13.1 Quality Control**

In accordance with applicable regulations including GCP, and GSK CH procedures, GSK CH or designee (i.e. third-party vendor) monitors will contact the site prior to the start of the study to review with the site staff the protocol, study requirements, and their responsibilities to satisfy regulatory, ethical, and GSK CH requirements.

When reviewing data collection procedures, the discussion will include identification, agreement and documentation of data items for which the CRF will serve as the source document.

GSK CH or designee will monitor the study and site activity to verify that the:

- Data are authentic, accurate, and complete.
- Safety and rights of subjects are being protected.

Property of GSK Consumer Healthcare - Confidential

May not be used, divulged, published or otherwise disclosed without the consent of GSKCH

SP1963/SOP-208661 : Template Version : 14 Mar 2019

- Study is conducted in accordance with the currently approved protocol and any other study agreements, GCP, and all applicable regulatory requirements.

The extent and nature of monitoring will be described in a written monitoring plan on file at GSK CH. The investigator (or designee) agrees to allow the monitor direct access to all relevant documents and agrees to co-operate with the monitor to ensure that any problems detected in the course of these monitoring visits are resolved.

## **13.2 Quality Assurance**

To ensure compliance with GCP and all applicable regulatory requirements, GSK CH may conduct a quality assurance assessment and/or audit of the site records, and the regulatory agencies may conduct a regulatory inspection at any time during or after completion of the study.

In the event of an assessment, audit or inspection, the investigator (and institution) must agree to grant the advisor(s), auditor(s) and inspector(s) direct access to all relevant documents and to allocate their time and the time of their staff to discuss the conduct of the study, any findings/relevant issues and to implement any corrective and/or preventative actions to address any findings/issues identified.

The investigator(s) will notify GSK CH or its agents immediately of any regulatory inspection notification in relation to the study. Furthermore, the investigator will cooperate with GSK CH or its agents to prepare the study site for the inspection and will allow GSK CH or its agent, whenever feasible, to be present during the inspection. The investigator will promptly apply copies of the inspection finding to GSK CH or its agent. Before response submission to the regulatory authority, the investigator will provide GSK CH or its agents with an opportunity to review and comment on responses to any such findings.

The sponsor will be available to help investigators prepare for an inspection.

## **13.3 Regulatory and Ethical Considerations**

### **13.3.1 Institutional Review Board/ Ethics Committee**

It is the responsibility of the investigator to have prospective approval of the study protocol, protocol amendments, informed consent documents, investigator brochure/safety statement (including any updates) and other relevant documents, e.g. recruitment advertisements, if applicable, from the IRB/EC. All correspondence with the IRB/EC should be retained in the investigator file. Copies of IRB/EC approvals should be forwarded to GSK CH prior to the initiation of the study, and also when subsequent amendments to the protocol are made.

The only circumstance in which an amendment may be initiated prior to IRB/EC approval is where the change is necessary to eliminate apparent immediate hazards to the subjects. In that event, the investigator must notify the IRB/EC and GSK CH in writing immediately after the implementation.

### **13.3.2 Ethical Conduct of the Study**

The study will be conducted in accordance with legal and regulatory requirements, as well as the general principles set forth in the International Ethical Guidelines for Biomedical Research Involving Human Subjects (Council for International Organizations of Medical Sciences 2002),

Property of GSK Consumer Healthcare - Confidential

May not be used, divulged, published or otherwise disclosed without the consent of GSKCH

SP1963/SOP-208661 : Template Version : 14 Mar 2019

---

International Ethical Guidelines for Health-Related Research Involving Humans (Council for International Organizations of Medical Sciences, 2016), guidelines for GCP (ICH 1996 and revision 2), and the Declaration of Helsinki (World Medical Association 2013).

In addition, the study will be conducted in accordance with the protocol, the ICH guideline on GCP, and applicable local regulatory requirements and laws.

### **13.3.3 Subject Information and Consent**

All parties will ensure protection of subject personal data and will not include subject names or other identifiable data in any reports, publications, or other disclosures, except where required by laws.

When study data are compiled for transfer to GSK CH and other authorised parties, subject names, addresses, and other identifiable data will be replaced by numerical codes based on a numbering system provided by GSK CH in order to de-identify study subjects.

The study site will maintain a confidential list of subjects who participated in the study, linking each subject's numerical code to his or her actual identity. In case of data transfer, GSK CH will maintain high standards of confidentiality and protection of subjects' personal data consistent with applicable privacy laws.

The informed consent documents must be in compliance with ICH GCP, local regulatory requirements, and legal requirements, including applicable privacy laws.

The informed consent documents used during the informed consent process must be reviewed and approved by the sponsor, approved by the IRB/EC before use, and available for inspection.

The investigator must ensure that each study subject, is fully informed about the nature and objectives of the study and possible risks associated with participation.

### **13.3.4 Subject Recruitment**

Advertisements approved by IRBs/ECs and investigator databases may be used as recruitment procedures. Use of ethics committee approved, generic, prescreening questionnaire to assess basic subject characteristics to determine general eligibility for this study is allowed. This generic questionnaire may be used by sites as a phone script and/or to review internal databases to identify subjects.

GSK CH will have an opportunity to review and approve the content of any study recruitment materials directed to potential study subjects before such materials are used.

### **13.3.5 Reporting of Safety Issues and Serious Breaches of the Protocol or ICH GCP**

Within GSK CH a serious breach is defined as a breach likely to affect to a significant degree the safety and rights of a subject or the reliability and robustness of the data generated in GSK CH-sponsored human subject research studies.

In the event of any prohibition or restriction imposed (i.e., clinical hold) by an applicable competent authority in any area of the world, or if the investigator is aware of any new information that might influence the evaluation of the benefits and risks of the investigational product, GSK CH should be informed immediately.

---

In addition, the investigator will inform GSK CH immediately of any urgent safety measures taken by the investigator to protect the study subjects against any immediate hazard, and of any serious breaches of this protocol or of ICH GCP that the investigator becomes aware of.

### **13.4 Posting of Information on Publicly Available Clinical Trial Registers**

Study information from this protocol will be posted on publicly available clinical trial registers before enrollment of subjects begins in accordance with applicable GSK CH processes.

GSK intends to make anonymized subject-level data from this trial available to external researchers for scientific analyses or to conduct further research that can help advance medical science or improve patient care. This helps ensure the data provided by trial participants are used to maximum effect in the creation of knowledge and understanding

### **13.5 Provision of Study Results to Investigators**

Where required by applicable regulatory requirements, an investigator signatory will be identified for the approval of the clinical study report. The investigator will be provided reasonable access to statistical tables, figures, and relevant reports and will have the opportunity to review the complete study results at a GSK CH site or other mutually-agreeable location.

GSK CH will also provide the investigator with the full summary of the study results. The investigator is encouraged to share the summary results with the study subjects, as appropriate.

The procedures and timing for public disclosure of the results summary and for development of a manuscript for publication will be in accordance with GSK CH Policy.

A manuscript will be progressed for publication in the scientific literature if the results provide important scientific or medical knowledge.

### **13.6 Records Retention**

Following closure of the study, the investigator must maintain all site study records (except for those required by local regulations to be maintained elsewhere), in a safe and secure location.

The records (study/ site master file) must be maintained to allow easy and timely retrieval, when needed (e.g. for a GSK CH audit or regulatory inspection) and must be available for review in conjunction with assessment of the facility, supporting systems, and relevant site staff.

Where permitted by local laws/regulations or institutional policy, some or all of these records can be maintained in a format other than hard copy (e.g. microfiche, scanned, electronic); however, caution needs to be exercised before such action is taken.

The investigator must ensure that all reproductions are legible and are a true and accurate copy of the original and meet accessibility and retrieval standards, including re-generating a hard copy, if required. Furthermore, the investigator must ensure there is an acceptable back-up of these reproductions and that an acceptable quality control process exists for making these reproductions.

The investigator must assure that the subject's anonymity will be maintained. On CRFs or other documents submitted to GSK CH, subjects should not be identified by their names or initials, but by an identification code. The investigator should keep a separate log of subjects' codes,

---

names and addresses. Documents not for submission to GSK CH, e.g. subjects' written consent forms, should be maintained by the investigator in strict confidence.

Records and documents, including signed ICF, pertaining to the conduct of this study must be retained by the investigator for 25 years from the issue of the final Clinical Study Report (CSR) or equivalent summary, unless local regulations or institutional policies require a longer retention period. The minimum retention time will meet the strictest standard applicable to that site for the study, as dictated by any institutional requirements or local laws or regulations, GSK CH standards/procedures, and/or institutional requirements.

No study document should be destroyed without a prior written agreement between GSK CH and the investigator. The investigator must notify GSK CH of any changes in the archival arrangements, including, but not limited to, archival at an off-site facility or transfer of ownership of the records in the event the investigator is no longer associated with the site.

### **13.7 Conditions for Terminating the Study**

Premature termination of this study may occur because of a regulatory authority decision, change in opinion of the IRB/EC, or study product safety problems, or at the discretion of GSK CH. In addition, GSK CH retains the right to discontinue developmental skin care products at any time.

If a study is prematurely terminated, GSK CH will promptly notify the investigator. After notification, the investigator must promptly contact all participating subjects and should assure appropriate therapy/ follow-up for the subjects. As directed by GSK CH, all study materials must be collected and all CRFs completed to the greatest extent possible. Where required by the applicable regulatory requirements, GSK CH should inform the regulatory authority(ies) and the investigator should promptly inform the IRB/EC and provide the IRB/EC a detailed written explanation of the termination or suspension.

If the IRB/EC terminates or suspends its approval/favorable opinion of a trial, the investigator should promptly notify the GSK CH and provide GSK CH with a detailed written explanation of the termination or suspension.

Upon completion or premature discontinuation of the study, the GSK CH monitor will conduct site closure activities with the investigator or site staff, as appropriate, in accordance with applicable regulations including GCP, and GSK CH Standard Operating Procedures.

## 15 APPENDICES

### 15.1 APPENDIX 1- ABBREVIATIONS

**Table 15-1** **Abbreviations**

Abbreviation	Term
AE	adverse event
CRF	case report form
cm 	Centimeter squared
EC	ethics committee
eCRF	Electronic Case Report Form
FSFV	First Subject First Visit
GCP	Good Clinical Practice
ICH	International Conference on Harmonisation

Property of GSK Consumer Healthcare - Confidential

May not be used, divulged, published or otherwise disclosed without the consent of GSKCH  
SP1963/SOP-208661 : Template Version : 14 Mar 2019

Abbreviation	Term
ID	identification
IEC	Independent Ethics Committee
IRB	institutional review board
IRC	internal review committee
LSLV	last subject last visit
MED	Minimal Erythema Dose
MedDRA	medical Dictionary for Regulatory Activities
mL	Milliliter
N/A	not applicable
PI	principal investigator
PT	Preferred Term
SAE	serious adverse event
SmPC	summary of product characteristics
SOC	System Organ Class
SOP	standard operating procedure
SRSD	single reference study document
SS	safety statement
UVR	Ultra Violet Radiation

## 15.2 Appendix 2- Scoring of patch test reactions according to ICDRG.

Patch testing techniques and scoring reactions by a grading scale were first standardized in the 1930s. The International Contact Dermatitis Research Group (ICDRG) published the following nonlinear, descriptive grading scale in 1970's ([Fregert, 1974](#)) which continues to be widely used and will be adopted for this clinical study Table 15-2. Therefore, any skin response at a patched site will be clinically assessed using scale recommended by the ICDRG.

A trained, blinded evaluator will score the test sites for signs of irritation per ICDRG scale at all time points specified in the study schedule. The evaluator score will be considered final.

For each subject who presents a positive reaction (i.e. a reaction score of '+' or greater) in the challenge phase a blinded dermatologist will further classify the reaction as potential sensitisation (or not) at the final visit and provide a single narrative description to summarise the entirety of the subject's experience of the event. As sensitisation and irritation can occur in the challenge phase, it is possible to record a positive reaction in the challenge phase which is not a sensitisation reaction. The dermatologist must consider how the reaction presents/evolves over time, to ascertain whether it is characteristic of a sensitisation reaction. The dermatologist will record their opinion in the narrative and with a check-box in the CRF.

The narrative must include the start and finish date of the event, a description of how the event evolves over time, any action taken (e.g. moved patch), and diagnosis (potential sensitisation reaction, or other as appropriate). If a clear diagnosis cannot be made, then the dermatologist should include this in the narrative.

**Table 15-2 Scoring of patch cells according to ICDRG**

-	Negative reaction
---	-------------------

+?	Doubtful reaction; faint erythema only
+	Weak (non-vesicular) positive reaction; erythema, infiltration and possibly papules
++	Strong (vesicular) positive reaction; erythema, infiltration, papules and vesicles
+++	Extreme positive reaction; bullous reaction, intense erythema and infiltration, coalescing vesicles
(IR)	Irritant reaction
(NT)	Not tested

If a subject develops a score of 'Strong' (++) or greater at any point during the induction phase, the next patch will be applied to an adjacent naïve (i.e. previously untreated) site. If a score of 'Strong' (++) or greater occurs at the naïve site, no further patch applications will be made. Such reactive subjects will, however, progress to the challenge phase unless, in the opinion of the Investigator, it would be unwise to do so.

Any dermal irritation or sensitisation reactions which occur within the patch application area and can't be completely described by the scale in Table 15-2 (Appendix 2), will not be recorded as AEs during the study. Reactions to the patch itself will also not be recorded as AEs. These responses are typical effects of occluded application of topical products.

Unexpected or unusual reactions which occur within the patch area that cannot be completely described by the scale in Table 15-2 (Appendix 2), (e.g., rash, hives) will be recorded as AEs.

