#### **Events NOT meeting the AE definition:**

- Any clinically significant abnormal laboratory findings (if applicable) or other abnormal safety assessments which are associated with the underlying disease, unless judged by the investigator to be more severe than expected for the subject's condition.
- The disease/disorder being studied or expected progression, signs, or symptoms of the disease/disorder being studied, unless more severe than expected for the subject's condition.
- Medical or surgical procedure (e.g. endoscopy, appendectomy) is not the AE. The condition that leads to the procedure is an AE (e.g. appendicitis).
- Situations where an untoward medical occurrence did not occur (social and/or convenience admission to a hospital).
- Anticipated day-to-day fluctuations of pre-existing disease(s) or condition(s) present or detected at the start of the study that do not worsen.
- Any cutaneous (dermal) irritation or sensitisation reactions which occur within the patch application area and can be completely described by the scale in [Appendix 2](#) will not be recorded as AEs. Reactions to the patch or adhesive tape will also not be recorded as AEs.

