## **10.2 Definition of a Serious Adverse Event (SAE)**

A Serious Adverse Event (SAE) is a particular category of an adverse event where the adverse outcome is serious. If an event is not an AE per definition above, then it cannot be an SAE even if serious conditions are met (e.g. hospitalisation for signs/symptoms of the disease under study, death due to progression of disease).

A serious adverse event is any untoward medical occurrence at any dose that:

- **Results in death**
- **Is life-threatening**
  - The term 'life-threatening' in the definition of 'serious' refers to an event in which the subject was at risk of death at the time of the event. It does not refer to an event, which hypothetically might have caused death, if it were more severe;
- **Requires inpatient hospitalisation or prolongation of existing hospitalisation**
  - In general, hospitalisation signifies that the subject has been detained (usually involving at least an overnight stay) at the hospital or emergency ward for observation and/or treatment that would not have been appropriate in the physician's office or outpatient setting. Complications that occur during

hospitalisation are AEs. If a complication prolongs hospitalisation or fulfills any other serious criteria, the event is serious. When in doubt as to whether “hospitalisation” occurred, or was necessary, the AE should be considered serious.

- Hospitalisation for elective treatment of a pre-existing condition that did not worsen from baseline is not considered an AE.
- **Results in persistent or significant disability/incapacity**
  - The term disability means a substantial disruption of a person’s ability to conduct normal life functions.
  - This definition is not intended to include experiences of relatively minor medical significance such as uncomplicated headache, nausea, vomiting, diarrhea, influensa, and accidental trauma (e.g. sprained ankle) which may interfere with or prevent everyday life functions but do not constitute a substantial disruption
- **Results in congenital anomaly/birth defect**
- **Other situations:**

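### Appendix 2 reverses the adverse-event rule for patch-area reactions, and the local-reaction exemptions in 10.1, read literally with 10.2, could leave a serious one outside SAE reporting

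*Protocol*

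**What the plan says.** **The scale exemption.** In Protocol Appendix 2, the notes under Table 15-2 state that patch-area irritation or sensitisation reactions that "can't be completely described by the scale in Table 15-2 (Appendix 2), will not be recorded as AEs during the study". The paragraph that follows takes "Unexpected or unusual reactions which occur within the patch area that cannot be completely described by the scale", gives rash and hives as examples, and makes them AEs. Sections 8.5.2 and 9.2.1 carry that same inclusion rule with the same two examples. For the exemption itself, 8.5.2, 9.2.1 and 10.1 use the opposite condition; in 10.1 it covers "Any cutaneous (dermal) irritation or sensitisation reactions which occur within the patch application area and can be completely described by the scale in" Appendix 2.

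**The patch and adhesive exemption.** A second exemption stands beside the first each time. In 10.1, under the list of events that do not meet the AE definition, it reads "Reactions to the patch or adhesive tape will also not be recorded as AEs". Appendix 2 has a shorter form: "Reactions to the patch itself will also not be recorded as AEs".

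**The step from AE to SAE.** Section 10.2 states: "If an event is not an AE per definition above, then it cannot be an SAE even if serious conditions are met". Its examples are "hospitalisation for signs/symptoms of the disease under study, death due to progression of disease". Section 10.4 has each AE assessed for seriousness, and 10.4.2 sets a 24-hour limit for the SAE form. SAP 4.6.1 tabulates and lists AEs and SAEs as recorded, with a skin/non-skin split taken from the AE page.

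**The concern.** There are two separate problems.

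First, Appendix 2 gives opposite instructions in consecutive paragraphs for a local reaction that falls outside the scale. The grading table is the page the evaluator works from, and under 5.8 and 9.2.1 that person need not be medically qualified.

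Second, neither exemption says what happens if an exempted reaction turns out to be serious. Because 10.1 places both groups outside the AE definition, the opening of 10.2 appears to close the SAE route for them.

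At stake are the safety endpoint in Table 3-1 (frequency and severity of AEs), the 24-hour report, the investigator's intensity and causality assessments under 10.5, and the SAE listings in SAP 4.6.1. Keeping routine patch reactions out of the AE tables is a deliberate choice with a stated reason, and it is not questioned here.

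**Working it through.** No arithmetic applies beyond counting statements, and no calculation was run. The protocol passages set side by side:

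| Place | Scale exemption: not an AE if the scale ... | Patch/adhesive exemption | Out-of-scale unexpected reactions are AEs | Seriousness exception |
|---|---|---|---|---|
| 8.5.2 | *can* describe it | patch and adhesive | yes (rash, hives) | none |
| 9.2.1 | *can* describe it | patch and adhesive | yes (rash, hives) | none |
| 10.1 | *can* describe it | patch and adhesive tape | not stated | none |
| Appendix 2 | ***can't*** describe it | patch only | yes (rash, hives) | none |

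**Step 1: the scale exemption.** There are four statements, three with *can* and one with *can't*. The inclusion rule for out-of-scale reactions appears three times, once directly below the *can't* sentence. Appendix 2 justifies its exemptions by saying such responses are typical of occluded application. That reason fits reactions the scale describes and does not fit unexpected ones. The documents therefore resolve the conflict themselves: *can* is the consistent word.

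**Step 2: the seriousness gap.** The two exemptions in four places make 4 + 4 = 8 statements, and none has a seriousness exception. These are the same two sentences repeated, so the count shows that the omission is uniform, not how large it is.

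**Step 3: the literal chain.**
1. The scale runs up to +++, which includes bullous reactions. A patch-area reaction of that grade that the scale completely describes is exempt under 10.1.
2. Under 10.2, an event that is not an AE is not an SAE, even if a seriousness condition is met.
3. Under 10.4, AEs are what is assessed for seriousness; under 10.4.2, the 24-hour clock applies to SAEs.

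A reaction inside an exemption that met a 10.2 criterion would then not be recorded as an AE or reported as an SAE.

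**Step 4: the neighbouring bullets in 10.1.** The list has six bullets. Bullets 1 and 2 stop applying when the event is more severe than expected; bullet 2 concerns signs or symptoms "of the disease/disorder being studied, unless more severe than expected for the" subject's condition. Bullet 3 keeps the underlying condition as an AE, bullet 4 covers non-occurrences, and bullet 5 covers only conditions that do not worsen. Bullet 6, on patch reactions, has no such clause, although its scale half is bounded by the requirement of complete description. The limits in bullets 1 and 2 concern severity, not seriousness, so the comparison is suggestive and no more.

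**Step 5: where the chain weakens.** The inclusion rule in 8.5.2, 9.2.1 and Appendix 2 has no limit by cause. An unexpected reaction to the patch or adhesive that goes beyond the scale and lies in the patch area is an AE under that rule, while the second exemption says it is not. The text is in tension there. Reactions outside the patch area are outside the scale exemption altogether.

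**The case against.** The strongest reply on Appendix 2 is that the slip is harmless. A reader might infer that hives would disappear from the AE tables. The documents do not support that: site staff would have to follow one sentence against three explicit instructions naming hives, one of them immediately below it. This stands, and it makes the first part a correction of wording.

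On seriousness, a reader might infer that 10.2 simply bars SAE status for any serious local reaction. That is too strong, for several reasons:

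- Sections 10.1, 10.2 and 10.4 agree with one another. The second part is a missing exception, not a contradiction.
- The scale exemption stops where the scale stops, and the inclusion rule can reach out-of-scale patch or adhesive reactions in the patch area.
- The 10.2 examples concern a disease under study, in a trial of healthy volunteers. They look like template text.
- Section 10.2 also calls complications during hospitalisation AEs, and asks for medical or scientific judgement on whether SAE reporting is appropriate in other situations.
- One can argue that a reaction with a serious outcome is not completely described by a scale of skin signs.

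All of this narrows the gap without closing it. No passage says that a serious outcome takes a reaction out of the scale exemption. The judgement clause sits in the same section as the sentence that requires AE status first, and nothing says which prevails.

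It is also true that such a reaction would not be invisible. Its ICDRG grade is listed under SAP 4.5.1, as is a narrative if it is positive in the challenge phase. Concomitant treatment and withdrawal are recorded (6.8, 7.1), and the sponsor may be told under 8.14 or 13.3.5. None of these is SAE reporting.

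**Conclusion.** Both parts hold, with different weight.

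The Appendix 2 sentence is wrong as written. It conflicts with its own next paragraph and with 8.5.2, 9.2.1 and 10.1. It is very likely a drafting slip with little practical effect, but it should not stay beside the scoring table.

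The seriousness gap exists on a literal reading. It is clearest for a reaction the scale completely describes. For the patch and adhesive exemption the text is in tension and is not a clear bar. The conclusion assumes that site staff apply 10.1 and 10.2 as written and do not use the judgement clause to override them. The documents give no rate for exempted reactions that meet a seriousness criterion; it may be zero. The reason to act is that expedited reporting should not depend on how staff reconcile these sentences.

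The primary and secondary endpoints rest on ICDRG scores and the dermatologist's classification, so they are unaffected. The exposure is confined to AE and SAE recording and the safety endpoint.

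**What to change.** 1. In the Appendix 2 notes, change *can't* to *can*, so that all four statements of the scale exemption agree with each other and with the inclusion rule.
2. In 10.1, state once that neither exemption applies to a reaction meeting a 10.2 seriousness criterion. Such a reaction is recorded as an AE and reported as an SAE, and any ICDRG score stays in the endpoint analysis. Cross-refer to this from 8.5.2, 9.2.1 and Appendix 2.
3. Qualify the sentence in 10.2 to match.

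The cost is one word, one sentence, three cross-references and one qualified sentence, in a protocol amendment with a memo to the site. The SAP needs no change, because these events would enter its existing AE tables and SAE listings. The downside is possibly a few more AE records.
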